## 6. TREATMENT PLAN

### 6.1 Agent Administration

Treatment will be administered on an outpatient basis. For all patients, atezolizumab is administered first, followed by CDX-1127 (varlilumab). For patients on Arm A and on infusion days, cobimetinib is to be taken prior to starting atezolizumab. Reported adverse events and potential risks are described in Section 10. Appropriate dose modifications are described in Section 7. No investigational or commercial agents or therapies other than those described below may be administered with the intent to treat the patient's malignancy.

| Regimen Description -Arm A |   |        |  |               |                   |
|----------------------------|---|--------|--|---------------|-------------------|
| Agent                      | Premedication; Precautions  | Dose   | Route  | Schedule**    | Cycle Length      |
| Atezolizumab               | Premeds are not permitted for the first infusion. If patient experiences an Infusion-Related Reaction (IRR), pre-medication with antihistamines may be administered for subsequent infusions at the discretion of the treating physician. | 840 mg | IV (Initial dose delivered over approximately 60 minutes. Subsequent infusions may be delivered over approximately 30 minutes if initial infusion is tolerated without infusion-associated AEs.) | Days 1 and 15 | 28 days (4 weeks) |
|                            |   |        |  |               |                   |

|   |  |       |    |                  |  |
|---|--|-------|----|------------------|--|
|   |  |       |    |                  |  |
| Cobimetinib   | Cobimetinib should be taken at the same time every morning. It can be taken with or without food*. | 60 mg | PO | Daily, Days 1-21 |  |
| 
* The patient will be requested to maintain a medication diary of each dose of medication. The medication diary will be returned to clinic staff at the end of each course (Appendix E). If patient misses a day, they should resume their normal dose/time the next day and not "make up" the missed dose. If patient is unable to take their dose within 4 hours of regularly scheduled time on the same day, that day's dose should be considered missed and not taken. Resume dosing at the next scheduled dose/time.
  |  |       |    |                  |  |

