| Grade 2 hepatic event, $\leq 5$ days

*includes:
AST/ALT is $>\text{ULN}$ to $\leq 3 \times \text{ULN}$ at baseline and increases to $>5 \times \text{ULN}$ to $\leq 10 \times \text{ULN}$ | Continue atezolizumab & CDX-1127 (varlilumab).

Monitor LFTs biweekly until values resolve to baseline values.  | Continue atezolizumab & CDX-1127 (varlilumab) and cobimetinib.

Monitor LFTs biweekly until values resolve to baseline values.   |  |
| Grade 2 hepatic event, $>5$ days

*includes:
AST/ALT is $>\text{ULN}$ to $\leq 3 \times \text{ULN}$ at baseline and increases to $>5 \times \text{ULN}$ to $\leq 10 \times \text{ULN}$     | Hold atezolizumab & CDX-1127 (varlilumab).

Work to evaluate etiology of hepatic event. Consider patient referral to GI specialist for evaluation and liver biopsy to establish etiology of hepatic injury

If suspicion for immune-mediated process is high, initiate treatment with 1–2 mg/kg/day oral prednisone or equivalent.

If event resolves to grade 1 or better within 12 weeks, taper corticosteroids and resume atezolizumab according to the guidelines above.

Permanently discontinue atezolizumab & CDX-1127 (varlilumab) if event does not resolve to | Hold atezolizumab & CDX-1127 (varlilumab) and cobimetinib.

Work up to evaluate etiology of hepatic event. Consider patient referral to GI specialist for evaluation and liver biopsy to establish etiology of hepatic injury

If suspicion for immune-mediated process is high, initiate treatment with 1–2 mg/kg/day oral prednisone or equivalent.

If event resolves to grade 1 or better within 12 weeks, taper corticosteroids and resume atezolizumab & CDX-1127 (varlilumab) at fixed doses and cobimetinib at 1 dose reduction. |  |

|                            |  |  |
|----------------------------|--|--|

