|                            | 
Grade 1 or better within 12 weeks.
 
Resumption of atezolizumab atezolizumab & CDX-1127 (varlilumab) and cobimetinib at 1 level dose reduction may be considered in patients who are deriving benefit and have fully recovered from the immune-mediated event. The decision to re-challenge patients with atezolizumab & CDX-1127 (varlilumab) and cobimetinib should be based on investigator's assessment of benefit-risk, discussion with PI, and documented by the investigator (or an appropriate delegate)
 | 
Permanently discontinue atezolizumab & CDX-1127 (varlilumab) and cobimetinib if event does not resolve to Grade 1 or better within 12 weeks.
 
Resumption of atezolizumab atezolizumab & CDX-1127 (varlilumab) and cobimetinib at 1 level dose reduction may be considered in patients who are deriving benefit and have fully recovered from the immune-mediated event. The decision to re-challenge patients with atezolizumab & CDX-1127 (varlilumab) and cobimetinib should be based on investigator's assessment of benefit-risk, discussion with PI, and documented by the investigator (or an appropriate delegate)
 |
| Grade 3 or 4 hepatic event | 
Permanently discontinue atezolizumab & CDX-1127 (varlilumab)
 
Consider patient referral to GI specialist for evaluation and liver biopsy to establish etiology of hepatic injury.
 
If suspicion for immune-mediated process is high, initiate treatment with 1–2 mg/kg/day oral
   | 
Permanently discontinue atezolizumab & CDX-1127 (varlilumab) and hold cobimetinib.
 
Consider patient referral to GI specialist for evaluation and liver biopsy to establish etiology of hepatic injury.
 
If suspicion for immune-mediated process is high, initiate treatment
   |

|  |   |   |
|--|---|---|

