|  | 
prednisone or equivalent.
 
If event does not improve within 48 hours after initiating corticosteroids, consider adding an immunosuppressive agent.
 
If event resolves to grade 1 or better, taper corticosteroids over <math>\geq 1</math> month.
 
Resumption of atezolizumab atezolizumab & CDX-1127 (varlilumab) may be considered in patients who are deriving benefit and have fully recovered from the immune-mediated event. The decision to re-challenge patients with atezolizumab should be based on investigator's assessment of benefit-risk and documented by the investigator (or an appropriate delegate). For grade 3 AEs, patient may only resume after consultation with the trial PI; for grade 4, patient cannot resume treatment, regardless of benefit.
 | 
with 1–2 mg/kg/day oral prednisone or equivalent.
 
If event does not improve within 48 hours after initiating corticosteroids, consider adding an immunosuppressive agent.
 
If event resolves to grade 1 or better, taper corticosteroids over <math>\geq 1</math> month.
 
Resumption of atezolizumab atezolizumab & CDX-1127 (varlilumab) and cobimetinib at 1 level dose reduction may be considered in patients who are deriving benefit and have fully recovered from the immune-mediated event. The decision to re-challenge patients with atezolizumab & CDX-1127 (varlilumab) and cobimetinib should be based on investigator's assessment of benefit-risk and documented by the investigator (or an appropriate delegate). For grade 3 AEs, patient may only resume after consultation with the trial PI; for grade 4, patient cannot resume treatment, regardless of benefit.
 |
|--|---|---|

|               |              |   |   |
|---------------|--------------|---|---|

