## 9.5 Reporting and Exclusions

### 9.5.1 Evaluation of Toxicity

All patients will be evaluable for toxicity from the time of their first treatment with cobimetinib, atezolizumab, and CDX-1127 (varlilumab). A baseline measurement and at least 1 laboratory or other safety-related measurement obtained after at least 1 dose of study treatment may be required for inclusion in the analysis of a specific safety parameter (e.g., lab shifts from baseline). A complete list of all AE data will be provided along with an assessment of NCI CTCAE grade and relationship to study drug. The incidence of AEs will be tabulated by subgroups of interest (e.g. grade 3 or higher, organ class, relationship to study drug). For analyses at the individual level, the highest grade and relationship to study drug will be assumed if multiple events have occurred. Toxicity will be tabulated by type and grade and will be summarized with descriptive statistics. Other safety data will be assessed in terms of physical examination, clinical chemistry, hematology, vital signs, and ECGs. Negative binomial regression and Cox proportional hazards models will be used to assess the rate of AE and time to first toxicity, respectively.

While the combination of our proposed three study medications (or similar in-class alternatives) have not been studied in human trials, CDX-1127 (varlilumab) has been shown to be well tolerated in combination with anti-PD1, Nivolumab in patients with advanced solid tumors (NCT02335918). Additionally, the combination of cobimetinib and atezolizumab demonstrated a favorable safety profile at full doses in BTC patients (CTEP 10476). The present study will be continuously monitored for adverse events.

We will incorporate the following safety run-in and stopping rule that will be applied within each treatment group, A and B, respectively: if 2 or more “unacceptable toxicities,” at least possibly attributable to study therapy, are observed among the first 6 patients enrolled in the same treatment arm during their initial treatment cycle, we will pause the accrual in that arm and re-

evaluate safety. Accrual will be limited until the safety has been achieved in the first 6 patients in each arm, respectively.

“Unacceptable toxicities” are defined as the following treatment-related events:

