- Any grade  $\geq 2$  uveitis, retinitis, eye pain, or blurred vision that does not respond to topical therapy and does not improve to grade 1 severity within 2 weeks of starting therapy OR requires systemic treatment
- Recurrent grade 2 pneumonitis
- Symptomatic heart failure associated  $\geq 10\%$  reduction in LVEF
- Grade 3 uveitis, pneumonitis, bronchospasm, diarrhea, colitis, neurologic toxicity, hypersensitivity reaction, or infusion reaction
- Any grade 3 non-skin, drug-related AE lasting  $>7$  days, with the following exceptions:
  - Grade 3 endocrinopathies adequately controlled with only physiologic hormone replacement do not require discontinuation
  - Grade 3 laboratory abnormalities do not require treatment discontinuation except:
    - Grade 3 thrombocytopenia  $>7$  days OR that is associated with bleeding requires discontinuation
    - Any liver function test (LFT) abnormality that meets the following criteria require discontinuation:
      - Total bilirubin  $>3 \times$  ULN
      - Concurrent AST or ALT  $>3 \times$  ULN **and** total bilirubin  $>2 \times$  ULN
      - In participants with liver metastasis with baseline grade 2 elevation of AST or ALT, hepatitis with AST or ALT increases  $\geq 50\%$  and lasts  $\geq 1$  week
- Any grade 4 AE or laboratory abnormality, except for the following events which do not require discontinuation:
  - Grade 4 amylase or lipase abnormalities that are not associated with symptoms or clinical manifestations, or radiographic signs of pancreatitis. It is recommended to consult with the IND Sponsor for grade 4 amylase or lipase abnormalities.
  - Isolated grade 4 electrolyte imbalances/abnormalities that are not associated with clinical sequelae and are corrected with supplementation/appropriate management within 72 hours of their onset.
  - Grade 4 lymphopenia and leukopenia.
  - Grade 4 treatment-related endocrinopathy adverse events, such as adrenal insufficiency, ACTH deficiency, hyper- or hypothyroidism, or glucose intolerance, which resolve or are adequately controlled with physiologic hormone replacement (corticosteroids, thyroid hormones) or glucose-controlling agents, respectively, may not require discontinuation after discussion with and approval from the IND Sponsor.
- Any grade 5 adverse event
- Any dosing interruption lasting  $>6$  weeks with the following exceptions:
  - Dosing interruptions to allow for prolonged steroid tapers to manage drug-related adverse events are allowed.

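### The 2-of-6 run-in count in Section 9.5.1 leaves out an isolated Grade 3 AST/ALT rise recorded as a laboratory finding, although Section 7.3 permanently discontinues both antibodies for a Grade 3 hepatic event

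*Combined protocol and SAP*

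**What the plan says.** Section 9.5.1 sets a safety run-in for each arm. Two unacceptable toxicities are enough to pause accrual. Each must be judged possibly related to treatment or more strongly so, and the rule applies when they "are observed among the first 6 patients enrolled in the same treatment arm during their initial treatment cycle". It adds: "Accrual will be limited until the safety has been achieved in the first 6 patients in each arm".

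One item in the definition begins "Any grade 3 non-skin, drug-related AE lasting" and requires a duration of more than 7 days. Its exceptions include the line "Grade 3 laboratory abnormalities do not require treatment discontinuation except". Three liver-test patterns are then restored:

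- total bilirubin above 3 x ULN;
- AST or ALT above 3 x ULN together with total bilirubin above 2 x ULN;
- in a patient with liver metastasis and baseline Grade 2 enzymes, a rise of at least 50% lasting at least a week.

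Grade 4 laboratory abnormalities are a separate item, and AST/ALT is not among its exceptions.

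Section 7.3 has a row headed "Grade 3 or 4 hepatic event". It permanently discontinues atezolizumab and CDX-1127 in both columns and, for the triplet arm, also holds cobimetinib. Rechallenge requires full recovery, and "For grade 3 AEs, patient may only resume after consultation with the trial PI". Section 6.1 sends the reader to Section 7 for dosing: "Appropriate dose modifications are described in Section 7".

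**The concern.** The run-in is the only pre-specified rule that turns early toxicity into an accrual pause, and one arm is a first-in-human triplet (Section 2.3.4). An event serious enough for Section 7.3 to end both antibodies by default would be expected to count. On the layout of Section 9.5.1, one kind does not: a Grade 3 enzyme rise without the listed bilirubin rise, entered as a laboratory finding. Read literally, the same line also says that such a rise does not require discontinuation, which disagrees with Section 7.3.

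At stake is whether a pause for early hepatic toxicity follows from the written rule or depends on someone choosing to call it.

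**Working it through.** The plan gives no operating characteristic for the 2-of-6 rule, so there is no stated figure to reproduce. The check has two parts: following one event through both sections, then an illustration of size.

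**1. The event in Section 9.5.1.** Take a treatment-related Grade 3 ALT rise in cycle 1, from a normal baseline, bilirubin at or below 2 x ULN, entered as a laboratory abnormality.

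- General Grade 3 item: removed by the laboratory exception.
- First and second restored patterns: not met, since both need bilirubin above 2 x ULN or higher.
- Third restored pattern: not met without baseline Grade 2 enzymes. Section 3.1.5 caps AST/ALT at 3 x ULN at entry, so this pattern should rarely apply. That assumes Grade 2 begins above 3 x ULN; the documents do not print the cut-point.
- Grade 4 item: not met.
- Dosing interruption of more than 6 weeks: cannot be completed inside a 28-day first cycle.
- Permanent discontinuation is not itself a listed event.

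Result: not counted.

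**2. The same event in Section 7.3.** The hepatic rows are managed by liver tests, and the row "Grade 2 hepatic event" expressly includes cases defined by AST/ALT multiples alone. A hepatic event is therefore not confined to clinical hepatitis. At Grade 3 both antibodies are permanently discontinued. Two such patients among six give a run-in count of 0.

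**3. What is not in the gap.**

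- Grade 4 AST/ALT and the listed bilirubin patterns count.
- Immune-related hepatitis is listed in Section 10.1.1.1 as a hepatobiliary disorder, apart from transaminase rises under Investigations. If recorded that way and lasting more than 7 days, it could count.
- Patients whose baseline AST/ALT lay between ULN and 3 x ULN are managed as Grade 2 when they rise to more than 5 and up to 10 x ULN. The mismatch therefore falls mainly on patients with a normal baseline.

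**4. Illustration of size.** Let p be the per-patient probability of a counted toxicity in cycle 1, with at most one per patient. Then

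P(2 or more of 6) = 1 - (1 - p)^6 - 6p(1 - p)^5.

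For p = 0.10: 1 - 0.5314 - 0.3543 = 0.114. Suppose the uncounted events occur in patients with no other counted toxicity and add 2 or 5 points. All rates here are assumptions.

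| Assumed background | As written | +2 points | +5 points |
|---|---|---|---|
| 5% | 0.033 | 0.061 | 0.114 |
| 10% | 0.114 | 0.156 | 0.224 |
| 15% | 0.224 | 0.271 | 0.345 |

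With a 10% background the differences are about 4 and 11 points. If the two kinds of event are instead independent (combined rate p + q - pq, where q is the added rate), the 10% row becomes 0.151 and 0.212, so the combination rule matters little.

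These figures describe counting every such event. Deleting only the laboratory exception would bring back fewer, because the parent item still requires more than 7 days.

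**The case against.** The strongest reply is that the sections do different jobs. One pauses a cohort and the other manages a patient, and nothing in the protocol makes a Section 7.3 discontinuation the test for counting. Grade 2 immune-related myocarditis is also a permanent discontinuation and is not a listed run-in event by itself. The liver thresholds look deliberate: the combined enzyme and bilirubin pattern is close to the Hy's Law event of special interest in Section 10.3.4. A rule based on impaired liver function is coherent, and Grade 3 discontinuation has a rechallenge route.

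Much of this stands and limits the severity. It does not supply a reason for the omission. Section 9.5.1 counts Grade 3 diarrhea and colitis at any duration, although Section 7.3 only holds the drugs for these and allows resumption after recovery. The hepatic event has the harsher default and the weaker claim on the count.

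A reader might infer three stronger things that the documents do not support.

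- *Competing dosing orders.* The literal wording invites this, but Section 6.1 makes Section 7 the place for dose modification, and the line sits in a list of exceptions to a counting item.
- *A gap that can be sized from the cobimetinib phase 3 trial.* Section 2.2.2.2.3 reports Grade 3-4 ALT rises of 11% versus 5%, an excess of 6 points. That is a cobimetinib effect and says nothing about the doublet arm. It pools Grade 4 events, which already count, and it covers whole treatment in melanoma with vemurafenib. It also reflects neither the 7-day condition nor the raised-baseline rule. For Arm A it is at most a loose upper case, and it is not used here. Section 2.3.1 reports atezolizumab plus cobimetinib as tolerable in biliary cancer.
- *Absence of oversight.* The trial PI must be consulted before any Grade 3 rechallenge, AST/ALT above 10 x ULN is a cobimetinib event of special interest, adverse events are monitored continuously, and the DSMB oversees the study. These would probably notice two such patients. The separate accrual limit also leaves room for judgement, but it states no criterion beyond the 2-of-6 count.

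**Conclusion.** The concern holds as a minor gap in the formal run-in rule. By its placement, though not in so many words, the laboratory exception removes from the count a Grade 3 AST/ALT rise with bilirubin at or below 2 x ULN that is recorded as a laboratory finding, while Section 7.3 ends both antibodies for it by default. Both available readings need attention: as a counting exception the line omits a discontinuing event, and taken literally it contradicts Section 7.3.

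The size cannot be established, because the documents give no cycle-1 Grade 3 rate for either arm. The illustrated change, from 0.11 to 0.16 or 0.22 with a 10% background, rests on assumed rates and on added events falling in patients not otherwise counted. Existing oversight keeps the severity low.

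**What to change.** Add to the liver-test list in Section 9.5.1: *any treatment-related Grade 3 AST/ALT rise in cycle 1 for which both antibodies are permanently discontinued under Section 7.3 (counted even if later rechallenged)*. State in the same place that Section 7.3 governs dosing. If the clinical team considers such rises tolerable, amend the Section 7.3 hepatic row instead, so that the two sections agree.

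The cost is wording in one or two sections and a somewhat higher chance of an accrual pause with safety review: about 4 to 11 points per arm under the 10% background and the 2 to 5 added points assumed above. The new line carries no 7-day condition, so it is stricter than the general Grade 3 item; the link to permanent discontinuation is the reason for that. The documents do not say whether the run-in is complete. If it is, check the first six patients in each arm for such events.

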#### 6.1.1.3 Cobimetinib

Patients will receive cobimetinib at a dose of 60 mg (three tablets of 20 mg each) orally once daily for Days 1–21 of a 28-day cycle. This 4-week period is considered a treatment cycle. Guidelines for dosage modification and treatment interruption or discontinuation are provided in Section 7.

Cobimetinib should be taken in the morning at the same time every day. It can be taken with or without food. If a dose of cobimetinib is not taken within 4 hours of the scheduled dose, it should be considered missed and not taken. Resume dosing at the next scheduled dose. If vomiting occurs when the dose is taken, resume dosing with the next scheduled dose.

Patients receiving cobimetinib will be requested to maintain a medication diary (see Appendix E) of each dose of medication. The medication diary will be returned to clinic staff at the end of each course. The study team should review the diary for completeness and any inconsistencies and discuss them with the participant at the visit.

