## 7. DOSING DELAYS/DOSE MODIFICATIONS

### 7.1 CDX-1127 (varlilumab) and Atezolizumab (all participants)

#### 7.1.1 General AE Management and Dose Modification Guidelines

Dosing of both CDX-1127 (varlilumab) and atezolizumab is fixed with no dose-modification permitted. Both CDX-1127 (varlilumab) and atezolizumab should always be administered on the same day. Monotherapy with atezolizumab or CDX-1127 (varlilumab) alone is not permitted.

On cycle 1 day 1 (first dose), patients will be observed for at least 4 hours after the last study drug administration to monitor for infusion reaction/cytokine release syndrome/hypersensitivity reaction. For all subsequent doses/cycles, patients should be monitored for at least 1 hour following the last administration of study drug. Infusions should be given in a monitored setting that has ready access to an intensive care unit in case of a severe infusion reaction.

Acetaminophen may be used to manage drug-related adverse events such as fever, myalgias or arthralgias and anti-histamines may be used to manage drug-related adverse events such pruritus.

Patients may temporarily suspend study treatment for up to 84 days (12 weeks) beyond the scheduled date of delayed infusion if study drug-related toxicity requiring dose suspension is experienced. If atezolizumab and CDX-1127 (varlilumab) are held because of AEs for >84 days beyond the scheduled date of infusion, the patient will be discontinued from atezolizumab-CDX-1127 (varlilumab) and will be followed for safety and efficacy as specified in this protocol. If the AE resolves within 84 days and the patient is receiving corticosteroid therapy for the event, atezolizumab-CDX-1127 (varlilumab) may be held for longer than 84 days (up to 4 weeks) in order to allow tapering of the steroid dose to  $\leq 10$  mg oral prednisone or equivalent.

Dose interruptions for reasons other than toxicity, such as surgical procedures, may be allowed. The acceptable length of interruption will be at the discretion of the study PI in consultation with CTEP.

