  - Dosing interruptions  $>6$  weeks that occur for non-drug-related reasons may be allowed if approved by the Principal Investigator.
  - Prior to re-initiating treatment in a subject with a dosing interruption lasting  $>6$  weeks, the Principal Investigator must be consulted.

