## 11. STUDY CALENDAR

Informed consent is to be obtained any time prior to conducting research procedures and may be greater than 14 days before Randomization. Baseline timepoint scans, Echocardiogram (or MUGA), Eye Exam, and Pre-Treatment Biopsy are highly recommended to be done within 14 days of randomization but can be done up to a maximum of 28 days prior to randomization, if needed to accommodate scheduling limitations. Screening labs must be done within 14 days of randomization. In the event that the patient's condition is deteriorating, laboratory evaluations should be repeated within 48 hours prior to initiation of the next cycle of therapy. All participants receiving atezolizumab will be assessed for pulmonary signs and symptoms on physical examination as well as imaging throughout the study.

| 1 cycle = 28 days                   | Baseline                            | Cycle 1 |        |        | Cycle 2        |        |        | Cycle 3 and beyond |       |         | Progression/
End of
Treatment s |
|-------------------------------------|-------------------------------------|---------|--------|--------|----------------|--------|--------|--------------------|-------|---------|--|
|                                     |                                     | Day 1   | Day 15 | Day 21 | Day 1          | Day 15 | Day 21 | Day 28             | Day 1 | Day 15  |  |
| Visit window t           | -Day 14
to
Randomi-
zation | +/-2    | +/-2   | +/-5   | +/-2           | +/-2   | +/-5   | +/-2               | +/-2  | +/-5    | +14  |
| Atezolizumab b           |                                     | X       | X      | X      | X              | X      | X      | X                  | X     | X       |  |
| CDX-1127 (vanilimumab) c |                                     | X       | X      | X      | X              | X      | X      | X                  | X     | X       |  |
| Cobimetinib d            |                                     | X-----X |        |        | X-----X        |        |        | X-----X            |       | X-----X |  |
| Informed consent                    | X                                   |         |        |        |                |        |        |                    |       |         |  |

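### The run-in lists a dosing interruption of more than 6 weeks as a countable toxicity, but its 28-day counting window means the 2-of-6 pause rule can never count one

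*Combined protocol and SAP*

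**What the plan says.** The run-in rule in Section 9.5.1 applies to each arm separately. If 2 or more unacceptable toxicities, at least possibly attributable to study therapy, are seen among the first 6 patients "during their initial treatment cycle, we will pause the accrual in that arm", and safety is then re-evaluated. It adds: "Accrual will be limited until the safety has been achieved in the first 6 patients" of each arm.

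The same section then defines unacceptable toxicities as a list of treatment-related events. One entry is "Any dosing interruption lasting" more than 6 weeks. Its sub-items are:

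- An exemption for tapers: "Dosing interruptions to allow for prolonged steroid tapers to manage drug-related adverse events are allowed".
- Interruptions for reasons unrelated to the drug may be allowed if the Principal Investigator approves.
- A restart condition, beginning "Prior to re-initiating treatment in a subject with a dosing interruption lasting" more than 6 weeks, which requires that the Principal Investigator be consulted.

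Cycle length is fixed in two places. Section 6.1.1.3 says "This 4-week period is considered a treatment cycle", and the Section 11 calendar says "1 cycle = 28 days". Section 7.1.1 lets treatment be suspended for drug-related toxicity "for up to 84 days (12 weeks) beyond the scheduled date of delayed infusion", so holds well past 6 weeks are foreseen.

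**The concern.** The criterion needs more than 6 weeks and the counting window is 4 weeks. The sponsor placed the line in the list that the pause rule counts, in the trial's only numeric toxicity rule for pausing accrual, and Section 2.3.4 describes the triplet as first in human. If the line cannot fire, the rule is narrower than it appears. A patient held for two months for a toxicity that began in Cycle 1 would not count towards the 2 of 6 unless the event also met another line.

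**Working it through.** The plan states no operating characteristic for the 2-of-6 rule, so there is no figure to reproduce. The check is a day count followed by a comparison of lists.

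**Inputs.** Cycle 1 is Days 1 to 28 (Sections 6.1.1.3 and 11). The threshold is more than 6 × 7 = 42 days (9.5.1). Infusions fall on Days 1 and 15 (6.1.1.2). Cobimetinib is taken on Days 1 to 21, Arm A only (6.1.1.3). Holds are measured in days beyond the scheduled date of the delayed dose (7.1.1). Planned accrual is 4 patients/month (9.2), randomized 1:1 (9.1).

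**Longest hold visible by Day 28** = 28 − scheduled day of first missed dose.

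- Cobimetinib missed from Day 2: 28 − 2 = 26 days.
- Day 15 infusion missed: 28 − 15 = 13 days.
- Adding the widest on-treatment calendar window of 5 days gives 31 and 18 days. All are short of 42.

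**First day on which the hold exceeds 42 days** = scheduled day of first missed dose + 43.

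| First missed dose | Criterion first met | Days after Day 28 |
|---|---|---|
| Cobimetinib, Day 2 (Arm A only) | 2 + 43 = Day 45 | 17 |
| Infusion, Day 15 (either arm) | 15 + 43 = Day 58 | 30 |
| Cycle 2 Day 1 = Day 29 (toxicity late in Cycle 1) | 29 + 43 = Day 72 | 44 |

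The Day 2 row is the most generous case, because it counts the planned cobimetinib rest week (Days 22 to 28) as interruption.

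**Which long holds are lost.** Steroid tapers are exempt. Most grade 3 non-skin events over 7 days, most grade 4 events and all grade 5 events count under other lines. These events remain:

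- Grade 2 neuropathy: Section 7.1.2 allows a hold of up to 12 weeks and does not mandate steroids. 9.5.1 counts neurologic toxicity from grade 3.
- Isolated grade 2 AST/ALT rise beyond 5 days: 7.3 holds treatment, with steroids only on high suspicion of an immune-mediated process. The liver criteria in 9.5.1 mostly need a bilirubin rise.
- Grade 2 creatinine rise: 7.3 holds treatment, with steroids only if an immune cause is highly suspected.
- Grade 3 or asymptomatic grade 4 amylase/lipase: 7.3 holds treatment, with steroids only to be considered. 9.5.1 exempts these through its laboratory exceptions.

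**Enrolment before a late count.** The rate per arm is 4 ÷ 2 = 2 patients/month, with 30.4 days to a month:

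- 17 ÷ 30.4 × 2 = 1.1
- 30 ÷ 30.4 × 2 = 2.0
- 44 ÷ 30.4 × 2 = 2.9

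So roughly 1 to 3 more patients per arm could enrol between the end of a patient's Cycle 1 and the day the hold qualifies.

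**The case against.** Three arguments can be made for the plan.

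First, Cycle 1 might still be open. Section 7.1.1 speaks of delayed infusions, and the calendar keeps imaging on schedule regardless of treatment delays, so dosing can drift from calendar days. If a held Day 15 infusion prolongs Cycle 1, or if events count by onset, the criterion could work. No text says either, and the rule refers to events observed during the cycle. This shows that sites might improvise a workable reading, not that the plan provides one.

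Second, the list has two purposes. Several entries speak of requiring discontinuation, and this bullet's sub-items concern individual patients. That stands: the bullet does operate as a restart rule. But 9.5.1 defines the whole list as the run-in's unacceptable toxicities, directly after the rule that uses the term.

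Third, little is lost in practice. This largely stands. Adverse events are monitored continuously, the Principal Investigator must be consulted before a restart after such a hold, and the DSMB can recommend closure. The rule itself only pauses accrual for re-evaluation.

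A reader might go further and infer that the run-in is unsafe, or that its chance of pausing is materially too low. The documents give no rate for such holds, so no pause probability can be calculated. A reader might also infer that most missed cases would surface before the sixth patient finishes Cycle 1. That depends on within-arm enrolment spacing, which the plan does not give, and a shift of a day or so in the count changes the answer. Grade 3 rash is not relied on here, because the duration line excludes skin events expressly.

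**Conclusion.** The rule is wrong as written, with limited consequence. The incompatibility of a threshold above 42 days with a 28-day window is certain on the text. It holds under the most generous start date and the widest visit window. The finding assumes that Cycle 1 means its stated 28 days and that the threshold must be reached within it. The documents support that reading and state no alternative.

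The loss is confined to long, non-steroid, treatment-related holds for events such as those listed above. How often they would occur is unknown. This is one inoperative trigger in a rule whose other triggers work. It does not show that the run-in would fail to detect serious toxicity.

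**What to change.** Add one sentence to 9.5.1, attached to this bullet only: *An interruption caused by a treatment-related toxicity with onset in Cycle 1 counts towards the 2-of-6 rule if it later exceeds 6 weeks beyond the scheduled date of the first missed dose.* Leave the window for every other line unchanged. Keep the exceptions for steroid tapers and for approved non-drug reasons. State that accrual is not held to wait for such a case, and that the same pause applies if a late case brings the arm's count to 2.

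The change needs no extra patients or assessments. Its cost is that clearance of the first 6 patients stays provisional for some weeks while any hold that began in Cycle 1 is still running, and a pause may come after Cycle 1 ends. Roughly 1 to 3 more patients per arm could enrol in the interval at the planned overall rate, and fewer while run-in accrual is limited. Under the current wording such a case would not contribute to a pause at all.
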